6.0 Multi-Site Research (Multisite/Multicenter Only)

- 6.1 If this is a multi-site study where you are the lead investigator, describe the processes to ensure communication among sites, such as:
 - All sites have the most current version of the protocol, consent document, and HIPAA authorization.
 - All required approvals have been obtained at each site (including approval by the site's IRB of record).
 - All modifications have been communicated to sites, and approved (including approval by the site's IRB of record) before the modification is implemented.
 - All engaged participating sites will safeguard data as required by local information security policies.
 - *All local site investigators conduct the study appropriately.*
 - All non-compliance with the study protocol or applicable requirements will reported in accordance with local policy.

Response:

N/A – not a multicenter study

- 6.2 Describe the method for communicating to engaged participating sites:
 - Problems.
 - Interim results.
 - The closure of a study

Response:

N/A – not a multicenter study

7.0 Study Timelines

7.1 Describe the duration of an individual subject's participation in the study.

Response:

The study is composed of five phases: medical history qualification (eight weeks), lead-in (four weeks), titration (six weeks), study period (12 weeks), and taper (two weeks).

7.2 Describe the duration anticipated to enroll all study subjects.

Response:

1-2 years

7.3 Describe the estimated date for the investigators to complete this study (complete primary analyses)

Response:

06/2016

8.0 Study Endpoints

8.1 Describe the primary and secondary study endpoints.

Response:

The endpoints of this study are:

Primary Efficacy Endpoint:

• Comparison between lamotrigine and placebo groups of the reduction of Ménière's vertigo attacks from baseline

Secondary Efficacy Endpoints:

- Comparison between lamotrigine and placebo groups of vertigo attacks:
- Responder rate: Percentage of patients with > 50% reduction in vertigo attack frequency during treatment vs. baseline
- Vertigo attack free rate analysis: Length of vertigo attackfree intervals, number and percentage of vertigo attack-free days per 28 days period, number and percentage of patients who are vertigo attack-free during the double blind phase
- Comparison between lamotrigine and placebo groups of hearing loss:
- Analysis of audiograms between baseline and end of the study
- Comparison between lamotrigine and placebo groups of symptom severity:
- Ménière's Disease Patients-Oriented Severity Index (MDPOSI)
- Tinnitus Handicap Inventory (THI) questionnaire
- Clinical Global Impression-Severity & Change
- Comparison between lamotrigine and placebo groups of quality of life:
- Dizziness Handicap Inventory (DHI) questionnaire
- AAO-HNS Ménière's disease self-assessment

- Patient Health Questionnaire-9 (PHQ-9)
- Generalized Anxiety Disorder 7-item scale (GAD-7)

8.2 Describe any primary or secondary safety endpoints.

Response:

N/A – no such endpoints

9.0 **Procedures Involved**

9.1 Describe and explain the study design.

Response:

This is a randomized double-blind pilot proof-of-concept clinical trial. The principal investigator and all staff involved in clinic visits will remain blinded until the blind is scheduled to be broken or there is an emergency.

Participants who are diagnosed with Ménière's disease, as determined by clinical history, ENT confirmation and an audiogram, will qualify if they also have had two or more Ménière's vertigo attacks in a four-week span for two consecutive four-week periods (the qualification period). Those who meet these criteria will then need two or more Ménière's vertigo attacks during a four-week lead-in period to further establish a baseline and verify randomization eligibility. Participants are allowed from the beginning of the lead-in to take their choice of a symptomatic abortive medication according to its package instructions for Ménière's vertigo attacks that last longer than 30 minutes with nausea and/or vomiting. Symptomatic abortive medications include, but are not limited to, meclizine (Antivert), Valium, diazepam, or Zofran. The abortive medication can be used throughout the study regardless of treatment assignment and its use will be recorded. Twelve eligible participants, with a minimum total of six attacks during the qualification and lead-in periods, will be randomly assigned to either a placebo or lamotrigine treatment group. Randomization will be conducted by UBSoPPS Research Pharmacy. The study drug and matching placebo will be titrated from 25mg twice a day (BID) up to 150mg BID over a six week period. During titration, clinic visits are scheduled every two weeks to assess any adverse events, symptoms, quality of life, and compliance. Those who cannot tolerate the 150mg BID dose may return to a 100mg BID dose during an unplanned visit. However, if a participant is unable to tolerate the 100mg BID dose they will be withdrawn from the study. Participants will maintain the 150mg BID or 100mg BID dose for a 12-week period with clinic visits every four weeks to assess their progress. Between all study visits, participants are asked to complete a daily survey describing their symptoms. This survey is hosted by polleverywhere.com and can be completed through text message, an online website, or with a paper document- whatever method is preferred by the participant. At the conclusion of the 12-week study period, a study staff will be un-blinded

and will give participants assigned to the lamotrigine group the option to continue the study medication as a long-term open-label use outside of the study or to begin a two-week taper off. The number of participants who decide to continue the study medication will be noted, but the participant will be terminated from the study and thus responsible for all following costs. Those assigned to the placebo treatment will be informed of their treatment assignment and terminated from the study.

9.2 Provide a description of all research procedures being performed and when they are performed, including procedures being performed to monitor subjects for safety or minimize risks.

Response:

Please note: these procedures are a continuation from section 3.2, where section 3.2 outlines the screening procedures that are also part of standard medical care, and this section, section 9.2, is specific to research-only procedures.

At Visit 2, after the four week lead-in, inclusion/exclusion criteria will be re-evaluated. This includes a review of any concomitant medications. Participants will be asked to hand in their Ménière's survey if they opted for the paper document. The surveys will be reviewed to ensure that abortive measures were only used during the severe attacks, as instructed. The Principal Investigator will assess any possible adverse events and then staff will administer the questionnaire batch. If the participant is eligible for randomization, he/she will be assigned to either a placebo or lamotrigine treatment group. Assignment will be based on a randomization conducted by UBSoPPS Research pharmacists, and the participant will be considered "enrolled" in the study at this point, and from this point on, all medical services, except abortive medication(s) of the patient's choice) are study-related and are not billed to the patient's insurance. Both groups will receive an amber vial of 28 pills with instructions to take one pill twice a day. Those in the lamotrigine group will be taking 25mg BID while those in the placebo group will be taking encapsulated microcrystalline cellulose. A drug dosage log will also be given to participants and they will be asked to write down the number of pills taken. Participants will be advised to notify the Principal Investigator or study staff if they develop rashes or other side effects. If the principal investigator decides that the rash is medication related, the participant will immediately stop the medication, return for an early termination visit and be terminated early from the study. Serious adverse events requiring withdrawal and unrelated to rash will return for an early termination visit and begin a two-week taper. If at any visit a participant is found to be non-compliant with dosing instructions, the Principal Investigator will assess the situation and determine if early termination is required. If the participant is terminated, they will follow the same taper schedule and early termination visit required for those withdrawing due to adverse events other than rash. Staff members will also remind participants to complete the daily survey and how to do so.

Two weeks later at Visit 3, current medications and adverse events will be reviewed by the Principal Investigator. A staff member will collect the medication containers, conduct a pill count and collect and review the dosage log and daily Ménière's survey responses. If the participant is determined to be compliant the staff member will administer the questionnaire batch. Continuing participants will receive an amber vial of 28 pills with instructions to take one pill twice a day. The medication will either be lamotrigine 50mg BID or the matching placebo. Staff members will then hand out another dosage log and remind participants to complete the daily survey. Participants are asked to return in two weeks.

At Visit 4, current medications and adverse events will be reviewed by the Principal Investigator. A staff member will collect the medication containers, conduct a pill count and collect and review the dosage log and daily Ménière's survey responses. If the participant is determined to be compliant the staff member will administer the questionnaire batch. Continuing participants will receive an amber vial of 28 pills with instructions to take one pill twice a day. The medication will either be lamotrigine 100mg BID or the matching placebo. Staff members will then hand out another dosage log and remind participants to complete the daily survey. Participants are asked to return in two weeks.

At Visit 5, current medications and adverse events will be reviewed by the Principal Investigator. Participants will complete another physical and neurological exam, a comprehensive audiogram with tympanometry, and a urine pregnancy test for females of reproductive age (<50yrs). Blood will be drawn, centrifuged and shipped to Kaleida Health's labs to analyze study drug levels. Additionally, a urine sample will be obtained for 24 hour creatinine clearance analysis as a screening measure for healthy kidney and liver function, to verify participants' ability to continue in the study. Study drug level results will be separated from other testing results and sent to UBSoPP Research Pharmacy to hold until the blind is broken and compliance can be reviewed. A staff member will collect the medication containers, conduct a pill count and collect and review the dosage log and daily Ménière's survey responses. If the participant is determined to be compliant, the staff member will administer the questionnaire batch. Continuing participants will receive an amber vial of 56 pills with instructions to take one pill twice a day. Participants' clinical response and tolerability will be assessed and if a participant reports no serious side effects from medications, the study drug will be further titrated to 150 mg BID or the matching placebo. If the participant finds that they cannot tolerate the 150mg BID dose, they are able to come into the clinic for an unscheduled visit and decrease to 100mg BID. Staff members will then hand out another dosage log and remind participants to complete the daily survey. Participants are asked to return in four weeks.

At Visit 6, current medications and adverse events will be reviewed by the Principal Investigator. A staff member will collect medication containers, conduct a pill count and collect and review the dosage log and daily Ménière's survey responses. If the participant is determined to be compliant the staff member will administer the questionnaire batch. Continuing participants will receive an amber vial of 56 pills of the same dosage, either 150mg BID or 100mg BID, with instructions to take one pill twice a day. Staff members will then hand out another dosage log and remind participants to complete the daily survey. Participants are asked to return in four weeks.

At Visit 7, current medications and adverse events will be reviewed by the Principal Investigator. A staff member will collect medication containers, conduct a pill count and collect and review the dosage log and daily Ménière's survey responses. If the participant is determined to be compliant the staff member will administer the questionnaire batch. Continuing participants will receive an amber vial of 56 pills of the same dosage, either 150mg BID or 100mg BID, with instructions to take one pill twice a day. Staff members will then hand out another dosage log and remind participants to complete the daily survey.

Four weeks later participants return to the clinic for Visit 8, current medications and adverse events will be reviewed by the Principal Investigator. The Principal Investigator will also administer a neurological and physical exam and complete the Clinical Global Impression-Severity and Change assessment. A staff member will collect medication containers, conduct a pill count and collect and review the dosage log and daily Ménière's survey responses. Participants will complete the questionnaire batch, and undergo a comprehensive audiogram with tympanometry. Blood will be drawn, centrifuged and shipped to Kaleida Health's labs to analyze study drug levels, CMP, CBC, and a urine pregnancy test will be conducted for female participants of reproductive age (<50yrs). Additionally, a urine sample will be obtained for 24 hour creatinine clearance analysis as a screening measure for healthy kidney and liver function. At the conclusion of the visit a staff member will be un-blinded by unsealing an envelope that contains treatment code and participant number. Those in the lamotrigine group will be given the option to be terminated from the study, but to continue the study medication at their own cost. Alternatively, they can continue in the study and begin to taper off the study drug. Those who decide to continue the study medication will be noted, but no further study participation is required. Participants continuing lamotrigine will be free to follow up on their treatment through the Dizziness and Balance Clinic or through a physician of their choice. Participants who decide to discontinue the study drug will begin a two-week taper consisting of one week at their current dosage QD and then one week of half the current dosage QD, and be paid for these 2 remaining study visits 9 and 10. Those assigned to the placebo group will be terminated from the study and are informed that they are allowed to seek treatment for their Ménière's disease at the Dizziness and Balance Clinic or elsewhere.

At both of the taper visits, participants will be given the tapered dose and asked to continue their dosage log. Staff will collect medication containers, conduct a pill count and review the dosage log to verify that participants are stopping the study drug in a safe manner. Any adverse events will continue to be reviewed by the Principal Investigator. At the last visit, participants will undergo one last physical and neurological exam and be notified of their termination from the study. At this point participants are informed that they are allowed to seek treatment for their Ménière's disease at the Dizziness and Balance Clinic or elsewhere.

9.3 Describe procedures performed to lessen the probability or magnitude of risks.

Response: Procedures to minimize risk of adverse events due to the drug are outlined in sections 9.2 and 12.7.

To provide detail sufficient detail on study procedures in reducing risk associated with the blood draws, I will copy Dent Neurologic Institute's official Blood Draw Policy here, which is adhered to by all employees of Dent who draw blood, including the research staff member assigned on our study team to draw blood.

POLICY & PROCEDURE

Title: Blood Draws Policy Number: CLN - 037

Category: Clinic Reference Statute, If one exists:

Standard: Approved By: CEO: [name], CEO

PURPOSE:

To provide accurate and complete instructions for safe blood drawing technique. **POLICY:**

It is the policy of the DNI to provide DENT staff with complete and accurate instructions for drawing blood.

RESPONSIBILITY:

It is the responsibility of the Clinic Managers to create and maintain the procedure. The DNI Clinic Staff need to be trained on this procedure.

PROCEDURE:

- 1.) Gather all necessary equipment;
- a.) Alcohol prep pads
- b.) Clean tourniquet
- c.) Clean disposal gloves sized appropriately
- d.) 4x4 gauze
- e.) Band-Aid or tape
- f.) Tubes
- g.) Vacuum holder or syringe
- h.) Appropriate size blood draw needle or butterfly
- i.) Specimen labels
- j.) Plastic specimen bag
- 2.) Meet and greet patient

Blood Draws

Page 1 of 3

- 3.) Escort patient into phlebotomy room
- 4.) Identify patient by three identifiers name, DOB, address
- 5.) Explain procedure to patient
- 6.) Check with patient regarding possible allergy to latex .(If positive see additional

information)

- 7.) Wash your hands
- 8.) Inspect both arms of the patient for possible venipunture site.
- 9.) Apply tourniquet to arm as per instructions
- 10.) Prep skin with one alcohol prep
- 11.) Don clean gloves
- 12.) Palpate possible venipunture sites as per instructions
- 13.) Place needle to vacuum holder or attach butterfly to syringe.

14.) With bevel up insert needle into vein at 15 degree angle. Gently push appropriate vial

onto needle hub or draw back on syringe.

- 15.) Allow blood to flow into blood collection tube
- a.) Lavender tubes drawn prior to blue tubes due to additive and air in tubing.

b.) Invert each tube a total of at least three times to insure proper mixing of blood and additive.

16.) When blood has reached the appropriate level, gently remove tube and place second

tube on to needle hub. Continue to do this until all blood specimens have been collected. Draw enough blood in syringe if using butterfly to fill tubes.

17.) As last specimen is being obtained, remove tourniquet and complete the blood collection.

18.) Gently remove tube from needle setup. Remove needle and secure puncture site with gauze or cotton ball. 19.) Secure all specimens. 20.) Place Band-Aid over site. 21.) With patient still in the room: Label all specimens with correct label. Verbally verify patient's name and DOB as labels are attached to specimens. 22.) Complete appropriate paperwork, initials, time drawn. Blood Draws Page 2 of 3 23.) Discharge patient 24.) Place completed specimens and paperwork into to outgoing pickup and call Quest or LabCorp for pick up. 25.) Clean area 26.) Wash your hands 27.) Only three attempts are to be done. If unable to secure specimens after three attempts. must have another professional attempt. Blood Draws Page 3 of 3

9.4 Describe all drugs and devices used in the research and the purpose of their use, and their regulatory approval status.

Response:

Lamotrigine is a FDA approved drug for treating epilepsy and bipolar disorder, indicated as "schedule: N" – not subject to the Controlled Substances Act. The present study is exploring a new indication for Lamotrigine. The FDA has concluded that the study meets all of the requirements for exemption from the IND regulations and, therefore, an IND is not required to conduct the investigation (proof of this indication has been previously submitted to IRB)

The drug supply will be sent to the University of Buffalo's School of Pharmacy and Pharmaceutical Sciences (UBSoPPS) Research Pharmacy. Once it arrives the packing slip will be checked for completeness and then the study staff will be notified of its arrival. The invoice and inventory taken will be faxed over to the study site. The drugs will then be stored in their original containers in a room-temperature, dry and dark area of the UBSoPPS Research Pharmacy's lab, which has very limited access since it is a pharmacy. Temperature and humidity will be monitored by a UBSoPPS Research Pharmacist.

UBSoPPS Research Pharmacy will take the manufacture supplied tablet and place it inside a capsule. The capsule will be filled with methylcellulose until the entire content of the capsule is filled, decreasing the chance for un-blinding, and the capsule then closed. The encapsulated lamotrigine will then be packaged in an amber vial with a study label. Repackaging will follow NYS regulation. Repacking will be conducted by a pharmacist or under his/her immediate and personal supervision. A repacking record shall be maintained for five years, including the name, strength, lot number, quantity and name of the manufacturer and/or distributor of the drug repacked, the date of repacking, the number of packages prepared, the number of dosage units in each package, the signature of the person performing the repacking operation, the signature of the pharmacist who supervised the repacking, and such other identifying marks added by the pharmacy for internal recordkeeping purposes. Drugs repacked shall have an expiration date 12 months, or 50 percent of the time remaining to the manufacturer's expiration date, whichever is less, from the date of repacking.

SUNY at Buffalo School of Pharmacy and Pharmaceutical Sciences (UBSoPPS) Research Pharmacy will randomize eligible participants through www.randomizer.org. An UBSoPPS pharmacist will generate 12 random sets of numbers, ranging from 1-2 for the two assignment groups, with one unique number per set. UBSoPPS Research Pharmacy will use this randomization to compile a master log with the participant number and treatment code.

Those assigned to the lamotrigine treatment will take encapsulated lamotrigine daily for the duration of 20 weeks, consisting of a six-week titration, 12-week study period, and two-week taper. Possible doses for patients are 25mg BID, 50mg BID, 100 mg BID and 150mg BID during titration; 150mg BID or 100mg BID for the 12-week study period; 150mg QD or 100mg QD for Week 1 of the taper; and 75mg QD, or 50mg QD for Week 2 of the taper. Each increase in dose will be maintained for two weeks before deciding to further increase or decrease based on tolerability. Patients who discontinue at any point of the study will have a two-week taper consisting of the current dose QD for one week followed by half the dose QD for another week.

9.5 Describe the source records that will be used to collect data about subjects. (Attach all surveys, scripts, and data collection forms.)

Response:

- □ Ménière's Disease Patients-Oriented Severity Index (MDPOSI)
- □ Tinnitus Handicap Inventory (THI) questionnaire
- □ Clinical Global Impression-Severity & Change
- Dizziness Handicap Inventory (DHI) questionnaire
- □ AAO-HNS Ménière's disease self-assessment
- □ Patient Health Questionnaire-9 (PHQ-9)
- □ Generalized Anxiety Disorder 7-item scale (GAD-7)
- \Box Dosing Log
- □ Meniere's daily survey

9.6 What data will be collected including long-term follow-up.

Response:

Please see 9.5, plus:

 $\hfill\square$ Results of physical and neurological exams

- □ Audiogram
- \Box Drug dosing
- \Box CBC, CMP blood tests
- □ Lamotrigine blood levels (received from lab only after unblinding occurs)
- □ Urine pregnancy test results and creatinine levels
- \Box Drug adherence information
- □ Medications list
- □ Medical history
- 9.7 For HUD uses provide a description of the device, a summary of how you propose to use the device, including a description of any screening procedures, the HUD procedure, and any patient followup visits, tests or procedures.

Response: N/A

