11.0 Data Management

11.1 Describe the data analysis plan, including any statistical procedures.

Response: The primary response will be the number of vertigo attacks as measured at baseline and at the end of the study period. The secondary responses will include the percentage of vertigo free patients, audiograms, symptom severity scales and quality of life scales (listed in the Approach section). The analysis set will include all subjects who are randomized and receive at least one dose of the study medication or the placebo. Integer or continuous variables will be presented by their mean and median and their SD and IQR. Categorical variables will be summarized using counts and percentages. Demographic and baseline characteristics of the enrolled subjects will be summarized through descriptive statistics for continuous variables and through frequencies for categorical variables. Demographic and baseline characteristics of the intervention and placebo groups will be compared to assess for comparability. Continuous variables will be compared using Wilcoxon rank-sum test and categorical variables will be compared through Fisher's exact test. We will test for reduction in the Ménière's vertigo attacks from baseline through Wilcoxon's sign rank test and will compare the reduction between the two treatment groups using Wilcoxon rank-sum test. The tests will be two-tailed and the significance level will be set to 0.05. Additionally, we will perform statistical modeling of the number of vertigo attacks longitudinally through generalized linear mixed effects model using Poisson or Negative Binomial distribution as appropriate. Data analysis will be conducted using SAS (SAS Institute Inc., Cary, NC, USA) and R (http://www.r-project.org/). All data analyses will be performed by [name] of the SUNY UB Statistical Consultant Laboratory.

11.2 Provide a power analysis.

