Response: Safety information is collected at every visit; participants are asked about adverse events and complete questionnaires providing feedback on symptoms every visit throughout the duration of the study. Additionally, participants are encouraged to contact study personnel with any concerns, and are required to agree to report any degree of adverse health or psychological complaints regardless of whether or not they believe it is related to the study for the duration of the study including up to 28 days after their participation has concluded.

12.4 Describe the frequency of data collection, including when safety data collection starts.

Response: Data are collected at every visit; every 2 weeks for the first 10 weeks, then every 4 weeks from weeks 10 through 22, then two more visits separated by 1 week each. As previously stated, safety data are collected at every visit.

12.5 Describe who will review the data.

Response: Only the PI, Co-Investigator, Statistician, or Research Assistant at Dent Neurologic Institute will have access to the data and participant information. 12.6 Describe the frequency or periodicity of review of cumulative data.Response: Data will be reviewed bi-weekly.

12.7 Describe the statistical tests for analyzing the safety data to determine whether harm is occurring.

Response: I called IRB on 3/20/2015 to inquire about this and received verbal confirmation that the following procedures pertain to our study:

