Those assigned to the Lamotrigine treatment are at risk for rash, including Stevens-Johnson syndrome and toxic epidermal necrolysis, aseptic meningitis, hepatic and renal failure, DIC, arthritis, diplopia, sedation, dizziness, ataxia, headache, nausea and vomiting. Psychosis and depression are associated with epilepsy and occur in open label studies with all new AED's, but it is difficult to ascertain whether these relationships are causal. Incidence of rash was approximately 0.8% in adults receiving it as initial monotherapy for epilepsy and 0.08% in adults receiving it as initial monotherapy for bipolar and other mood disorders. This risk increases with concomitant valproate/divalproex use and reduces with slow titration. In order to prevent a rash, the daily dosage of lamotrigine will be slowly titrated by 50mg every two weeks. Valproate/divalproex, an anti-epileptic medication, is also prohibited from the study. If a study related rash does occur, the participant will be instructed to immediately discontinue the medication and to take an antihistamine drug. If the rash occurs with other serious symptoms associated with Stevens-Johnson syndrome and/or toxic epidermal necrolysis, such as fever, fatigue, sore throat, conjunctivitis or sores and/or ulcers in the mouth, lips or genital areas, participants are instructed to go to the emergency room. Hepatic and renal failure will be monitored with CBC and CMP blood analysis and a urine sample will be obtained for 24 hour creatinine clearance analysis as a screening, after titration and after the maintained dose period. Beginning with Visit 2, the C-SSRS will be conducted by a certified study staff to determine if there are any positive responses since last visit and whether it is safe for the participant to continue to participate in the trial. Any suicidal risk should be managed appropriately by the PI, who is a qualified mental health practitioner (MHP).

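### At Visits 3 to 7 the questionnaires are given only to participants judged compliant, so intermediate scores, and the last scores of those terminated for non-compliance, are missing by rule

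*Combined protocol and SAP*

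**What the plan says.** Section 9.2 describes each visit in turn. At Visits 3, 4, 6 and 7, after the pill count and review of the dosage log, the text reads "If the participant is determined to be compliant the staff member will administer the questionnaire batch". Visit 5 has the same sentence with a comma: "If the participant is determined to be compliant, the staff member will administer the questionnaire batch". The batches on either side carry no such condition. At Visit 2, before the first dose: "The Principal Investigator will assess any possible adverse events and then staff will administer the questionnaire batch". At Visit 8, the end of the 12-week study period: "Participants will complete the questionnaire batch, and undergo a comprehensive audiogram with tympanometry".

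Non-compliance does not by itself end participation. Under section 9.2, "the Principal Investigator will assess the situation and determine if early termination is required", and section 13.2 repeats that discretion. No pill-count percentage or other threshold defines compliance.

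Elsewhere the plan speaks of questionnaires without a condition. Section 12.3, on safety information, says that participants "complete questionnaires providing feedback on symptoms every visit throughout the duration of the study". Section 9.1 lists symptoms and quality of life among the things that titration visits assess. On analysis, section 11.1 states: "The analysis set will include all subjects who are randomized and receive at least one dose".

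The C-SSRS appears in section 3.2, in the screening series with the DHI, MDPOSI, Ménière's self-assessment, THI, PHQ-9 and GAD-7. Section 14.1 gives it a separate instruction: "Beginning with Visit 2, the C-SSRS will be conducted by a certified study staff". Section 9.2 does not name it, the source-record list in 9.5 omits it, and the content of the follow-up batch is never defined.

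**The concern.** The batch supplies most of the symptom-severity and quality-of-life measures behind the secondary objective. Compliance is observed after randomisation and may depend on treatment: a participant may miss doses because of side effects or because nothing seems to help. If scores are withheld when doses are missed, the missing scores may be related to outcome and may differ by arm. Since 11.1 analyses everyone randomised and dosed, and states no rule for missing scale scores, the analyst would face gaps that the protocol itself had created at visits the participant attended.

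The participants most exposed are those who leave early. They have no Visit 8 batch, so any scheduled post-baseline score must come from Visits 3 to 7, where the condition applies.

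**Working it through.** The plan gives no figure to reproduce here. The check is a count by visit, followed by a comparison of sections.

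**Step 1: count the conditional batches (section 9.2).**

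| Visit | Stage | Batch conditional on compliance? |
|---|---|---|
| 2 | Baseline, before first dose | No |
| 3 | Titration | Yes |
| 4 | Titration | Yes |
| 5 | End of titration | Yes |
| 6 | Study period | Yes |
| 7 | Study period | Yes |
| 8 | End of study period | No |

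Post-randomisation batches are at Visits 3 to 8, which is 6; those with the condition are at Visits 3 to 7, which is 5. So 5 of 6 are conditional. The taper visits are not counted, because 9.2 schedules no questionnaires there.

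**Step 2: follow a participant judged non-compliant.** Section 9.2 allows two outcomes.
- Kept in the study: as written, that visit's batch is not given. The participant stays in the analysis set with missing scores, although 12.3 says questionnaires are completed at every visit.
- Terminated: that visit's batch is likewise not given. An early termination visit follows, but no section says that it includes questionnaires. The nearest description, in 12.1 for termination of the whole study, covers a safety assessment, drug collection and adverse events. Under 13.3, nothing is collected once a participant chooses to withdraw. A participant terminated for non-compliance at Visit 3 would have no scheduled post-baseline score.

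**Step 3: list what is not conditional.** The Visit 2 and Visit 8 batches, the Clinical Global Impression at Visit 8, the audiograms at Visits 5 and 8, and the daily survey from which attacks are counted (9.1). The longitudinal model in 11.1 is for attack counts, not scale scores. Section 11.1 names no analysis time point for the scales, so whether the intermediate scores will be used is left open.

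**Step 4: scale.** No non-compliance rate is given, so only the weight of one participant can be stated. Assuming equal arms, a total of 12 gives 6 per arm and 1/6 = 16.7%; the total of 16 in the 11.2 update gives 8 per arm and 1/8 = 12.5%. Section 23.2 anticipates about 2 to 5 dropouts. Against 16 enrolled, that is 2/16 = 12.5% to 5/16 = 31.3% who might never reach Visit 8. Not all of them need be non-compliant.

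**The case against.** The strongest reply is that the visit text describes a sequence: those cleared to continue receive the batch and then their next supply, while the others go to early termination, so nobody who stays is skipped. That reading is available, and 12.3 leans towards it. It does not settle the matter. Section 9.2 uses a separate term for those continuing, and the condition is on compliance, not on continuation. Even on this reading, a terminated participant loses the scores of a visit that he or she attended.

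It can also be said that most of what a terminated participant loses comes from leaving, not from this sentence. That stands: the condition costs such a participant the scores of the terminating visit, and the undescribed early termination visit is a separate gap. It also stands that no passage shows non-compliance differing by arm; that is plausible, not demonstrated.

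Three stronger readings go beyond the documents. A reader might infer that the whole symptom and quality-of-life objective is measured in a selected subset, but the baseline and Visit 8 batches are unconditional. A reader might infer that the rule contradicts the analysis set in 11.1, but that set says who is analysed, not what is measured at each visit; the result is a missing-data problem. A reader might infer that the C-SSRS is skipped in non-compliant participants, but 14.1 requires it from Visit 2 with no compliance condition, and its place in the follow-up batch is only an inference from the screening list in 3.2.

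**Conclusion.** The point holds in a limited form. Taken as written, 9.2 makes five of six post-randomisation batches depend on an undefined judgement about behaviour after randomisation, and this conflicts with the every-visit statement in 12.3. What is lost is the intermediate scores of non-compliant participants who are kept, and the last-visit scores of those terminated for non-compliance. The practical weight falls on any longitudinal use of the scales and on early leavers.

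The size is unknown. The 12.5% to 16.7% is one participant divided by an assumed arm size of 8 or 6, not an expected loss. The conclusion rests on reading the visit text literally and on the investigator at least sometimes keeping, or terminating at a visit, someone judged non-compliant. The primary endpoint and the baseline-to-Visit-8 comparison in completers do not depend on it. On the C-SSRS, the finding is only that 3.2, 9.2 and 14.1 leave its relation to the batch unclear.

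**What to change.** At Visits 3 to 7 in section 9.2, delete the compliance condition. State that staff give the questionnaire batch to every participant who attends, whatever the pill count, and that this is done before any decision on continuation is acted on. Use the compliance check for that decision alone.

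Separately, list the contents of the follow-up batch, and reconcile 3.2, 9.2 and 14.1 on whether the C-SSRS is part of it, so that the visit text does not make conditional on compliance a scale that 14.1 requires without condition.

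The cost is one sentence at each of five visits and a short definition. No visit or instrument is added; the only burden is a few more questionnaires to administer and enter at visits already scheduled.
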